11.3.5.5 Subject's Global Assessment of Disease Severity

The subject's global assessment of disease severity will be summarised over time by treatment group.

11.3.6 Analysis of Safety

11.3.6.1 Adverse Events

The below analyses will be performed both for the open-label treatment phase safety analysis set for the open-label treatment phase and for the maintenance phase safety analysis set for the maintenance phase. For the maintenance phase safety analysis set for the maintenance phase, AEs will be presented by treatment group.

AEs will be coded during the course of the trial according to Medical Dictionary for Regulatory Activities (MedDRA). AEs will be presented by preferred terms and primary system organ class (SOC).

Treatment emergent AEs will be summarised, however all AEs recorded during the course of the trial will be included in the subject data listings. An event will be considered emergent with the trial treatment if started after the first application of IP or (applicable if there is a wash-out) if started before the first use of IP and worsened in severity thereafter. The tabulations described in the following will only include the events that are emergent with trial treatment. In each of the tabulations, AEs are defined by MedDRA preferred terms within primary SOC.

An overall summary of the number (percentage) of subjects with any treatment emergent AEs, SAEs, premature discontinuations from the trial due to AEs, treatment related AEs and severe AEs will be presented.

The number of AEs and the number of subjects experiencing each type of AEs will be tabulated by treatment group. The percentage of subjects with AEs will be compared between treatment groups by a chi-square test or Fisher's exact test (if expected cell count < 5).

The severity for each type of AE will be tabulated by treatment group..

The causal relationship to trial medication for each type of AEs will be tabulated by treatment group.

Related AEs are defined as AEs for which the (sub)investigator has not described the causal relationship to IPs as 'not related'. The number of related AEs and the number of subjects

experiencing each type of related AE will be tabulated. The percentage of subjects with related AEs will be compared between treatment groups by a chi-square test or Fisher's exact test (if expected cell count < 5).

The above tabulations will be done for the total maintenance phase, for the first 28 weeks of the maintenance phase, and for the remaining 24 weeks of the maintenance phase separately. An AE will be included in the tabulations by its start date. If an AE is ongoing at Visit 2 or Visit 9 and worsened in severity after, the AE will be included in the tabulations of both affected periods.

SAEs will be evaluated separately and a narrative for each will be given.

AEs leading to withdrawal from trial or discontinuation of IPs will be listed.

11.3.6.1.1 Adverse events associated with long term corticosteroid use

The AEs which have been judged by the adjudication committee to be associated with long term corticosteroid use will be listed along with information about demography and baseline characteristics.

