Assessment of target lesion/location is included as a complement to the PGA to capture information on severity of individual signs, i.e. redness, thickness and scaliness of target plaques. To document the development of response over time, target lesion/location photographs will be taken in a subset of patients recruited at one or a few selected sites equipped with adequate photographic equipment. Subjects will need to give a separate written consent for the collection of photographs. Even if they do not accept the collection of photographs, they may still participate in the main part of the trial.

One of the main objectives of this trial is to investigate the long-term safety of LEO 90100 over 56 (4 + 52) weeks, especially to evaluate the risk of corticosteroid-related cutaneous

adverse reactions and possible systemic effect during prolonged or repeated use of the product. The investigators will record all adverse events (AEs), and an independent adjudication panel of 2 dermatologists and one endocrinologist will review all treatment-emergent AEs (blinded data) to identify adverse drug reactions of concern associated with long-term topical corticosteroid use.

Because of the potential effect of vitamin D analogue containing products on calcium metabolism, there will be safety analyses of the parameters of calcium metabolism from blood and urine samples. As in previous LEO 90100 safety and efficacy trials, albumin-corrected serum calcium and spot urine calcium-creatinine ratio will be analysed in samples collected at baseline, Week 4 and at the end of trial.

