5.3 Safety assessments

- Adverse events of concern associated with long-term corticosteroid use
- Incidence of rebound (as defined in section [11.3.6.2](#))
- Local safety and tolerability assessment scores
- Effect on calcium metabolism, based on change from baseline in serum calcium and spot urinary calcium at Week 4 and the end of trial
- Effect on HPA axis (in a subset of subjects with disease involvement of between 10 and 30% of BSA), based on serum cortisol ≤ 18 mcg/dL 30 minutes after cosyntropin injection at Week 4, Week 28, and end of trial (Week 56) or early withdrawal.

[figure not shown]
Exposure and standard safety data will be reported as described in sections [11.3.3](#) and [11.3.6](#).

6 Trial Design

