5.5.3 Adverse Events

The adverse events (AEs) will be assigned to a specific period (e.g. open-label phase or randomised phase) based on the onset date the AE.

The long-term safety of LEO 90100 will be evaluated based on data from the randomised phase.

For treatment emergent adverse events (hereafter referred to as AEs) occurring in the randomised phase the following tables will be done:

Trial ID: LP0053-1004	Date: 15-JUL-2019	Version: 1.0 Page 31 of 177
-----------------------	-------------------	--------------------------------

An overall summary of AEs, SAEs, premature discontinuation from the trial due to AEs, treatment related AEs, severity of AEs, action taken with IMP and outcome of AEs will be presented. The summary will include number of events, number (percentage) of subjects and exposure rates.

The number of AEs, the number and percentage of subjects experiencing each type of AE, and the exposure rate will be tabulated by SOC and preferred term. The tabulation will be done for all treatment emergent AEs, for each type of severity separately, for related AEs, for serious AEs (SAEs), for non-serious adverse events, and for frequent AEs ($\geq 1\%$ in any treatment group).

All above tables will be done for the safety analysis set by treatment for the first 28 weeks of the randomised phase, and for the remaining 32 weeks of the randomised phase separately. In addition, the tables will be done for the safety analysis set by randomised treatment and rescue IMP for the total randomised phase, for the first 28 weeks of the randomised phase, and for the remaining 32 weeks of the randomised phase separately.

Further details for the tables can be found in [Appendix I](#) and [Appendix II](#).

Open-label phase:

For completeness, AEs for the open-label phase will be summarised separately as follows:

An overall summary of AEs, SAEs, AEs leading to withdrawal, treatment related AEs, severity of AEs, action taken with IMP and outcome of AEs will be presented. The summary will include number of events, number (percentage) of subjects and exposure rates.

The number of AEs, the number and percentage of subjects experiencing each type of AE, and the exposure rate will be tabulated by SOC and preferred term. The tabulation will be done for all treatment emergent AEs, for each type of severity separately, for related AEs, for serious AEs (SAEs), for non-serious adverse events, and for frequent AEs ($\geq 1\%$).

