5.5.3.1 Adverse events associated with long term corticosteroid use

Adverse events associated with long term corticosteroid use will be presented as described in the protocol.

Trial ID: LP0053-1004	Date: 15-JUL-2019	Version: 1.0 Page 33 of 177
-----------------------	-------------------	--------------------------------

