Appendix 2.7: Safety Data

Listing 7-1. Deaths

Listing 7-2. Serious Adverse Events

Listing 7-3. Subjects withdrawn from trial due to Adverse Events

Listing 7-4. Severe Adverse Events

Listing 7-5. Adverse Events

Trial ID: LP0053-1004	Date: 15-JUL-2019	Version: 1.0 Page 65 of 177
------------------------------	--------------------------	--------------------------------

Listing 7-6. Adverse Events Associated with Long Term Corticosteroid Use

Listing 7-7. Subjects Assessment of Local Safety and Tolerability

Listing 7-8. Investigators Assessment of Local Safety and Tolerability

Listing 7-9. Rebounds

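### The panel-adjudicated corticosteroid adverse events appear only in a listing, so no incidence or exposure-adjusted rate of that set by arm is pre-specified

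*Protocol*

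**What the plan says.** Protocol 3.3.3 states: "One of the main objectives of this trial is to investigate the long-term safety of LEO 90100", with emphasis on corticosteroid-related skin reactions and possible systemic effects. The same section sets up an independent panel, working on blinded data, "to identify adverse drug reactions of concern associated with long-term topical corticosteroid use". Protocol 12.1 describes it: two dermatologists and one endocrinologist review every treatment-emergent event. If they do not reach consensus, an event is kept even when only one member identified it.

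Protocol 5.3 includes "Adverse events of concern associated with long-term corticosteroid use" among the safety assessments.

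On analysis, Protocol 11.3.6.1.1 says the adjudicated events "will be listed along with information about demography and baseline characteristics". SAP 5.5.3.1 is one sentence: "Adverse events associated with long term corticosteroid use will be presented as described in the protocol". The matching output in SAP Appendix I is "Listing 7-6. Adverse Events Associated with Long Term Corticosteroid Use".

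For adverse events in general, SAP 5.5.3 says: "The tabulation will be done for all treatment emergent AEs, for each type of severity separately, for related AEs, for serious AEs", and adds non-serious and frequent events. These tables give subjects, percentages, events and rates per 100 patient-years.

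**The concern.** The trial creates a dedicated process to decide which events count as corticosteroid harm, then plans no summary of the result. A reader of the trial report would want to know how many subjects in each arm had an adjudicated event, and at what rate over exposure time. The plan does not commit to either figure.

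Row counts from a listing are a poor substitute. SAP 5.5.3 drops the between-arm tests on adverse events because early withdrawals might differ considerably between arms and longer follow-up raises the chance of seeing an event. The same reasoning applies to a hand count of adjudicated events. In addition, subjects in both arms receive LEO 90100 as rescue treatment, so whether an event began in remission or in relapse matters to its interpretation.

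If the summary is not specified before unblinding, any by-arm count of these events in the report will be post hoc.

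**Working it through.** The plan states no figure for this endpoint, so there is none to reproduce. The check is of the planned outputs, followed by an illustration of what a table could deliver.

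**Outputs.**
- Tables 3-1 to 3-70 in SAP Appendix I are the adverse event tables. Ten cover the open-label phase (3-1, 3-8, 3-15, 3-22, 3-29, 3-36, 3-43, 3-50, 3-57, 3-64). The other 70 − 10 = 60 are by randomised arm, some split further by rescue medication.
- None of Tables 3-1 to 3-110 and none of the adverse event shells (59 to 67) covers the adjudicated set. Listing 7-6 does.
- Three other items in Protocol 5.3 are tabulated by arm: rebound (Tables 3-71 and 3-72), local tolerability (3-75 to 3-78 and 3-81 to 3-84) and cortisol response (3-88 and 3-90).
- SAP 5.7, which records changes from the protocol, does not mention the adjudicated events.

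**Whether existing tables fill the gap.** The related-event tables (3-36 to 3-42) use the investigator's causality (Protocol 11.3.6.1; footnote to Shell 60). The panel judges independently, and its question is narrower: corticosteroid concern with at least a reasonable possibility of causation. The two sets can differ in both directions. The panel may include an event the investigator called unrelated, and it may leave out a related event that is not a corticosteroid effect. Preferred-term rows show single terms, and a subject with two terms appears in both, so the rows cannot simply be added to give the number of affected subjects.

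**Illustration.** The inputs are:
- Randomised, SAP Table 8: 132 + 55 + 52 + 68 + 56 + 68 + 114 = 545. At 1:1 this is about 272 per arm. The documents do not give the arm sizes or the safety-set sizes.
- Drop-out of 30% over 52 weeks, exponential (Protocol 11.1).
- Event counts of zero and five are assumptions, because the documents state no expected incidence.

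Zero events, complete follow-up, one-sided 95% bound: 1 − 0.05^(1/272) = 0.01095, or 1.1%. The upper end of a two-sided exact 95% interval is 1 − 0.025^(1/272) = 0.0135, or 1.3%. At the planned 190 per arm, the same two limits are 1.6% and 1.9%.

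Zero events, with drop-out, taking 52 weeks as one year: the drop-out hazard is −ln(0.7) = 0.3567 per year. Patient-years are 272 × (1 − 0.7)/0.3567 = 228.8. The one-sided 95% bound on the rate is −ln(0.05)/228.8 = 2.996/228.8 = 0.0131, or about 1.3 per 100 patient-years.

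Five affected subjects of 272: 5/272 = 1.8%, exact 95% interval 0.6% to 4.2%.

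**The case against.** The strongest reply is that little is lost. Every treatment-emergent event is tabulated by arm at preferred-term level with rates, and by remission or relapse, so the terms behind any adjudicated event can be found. Investigator-related events get the same treatment. The systemic side is covered in part by the cortisol tables, in the HPA subset. Denominators and patient-years by arm are planned, so a count can be assembled from the listing. Protocol 3.3.3 calls pathologic adrenal suppression very rare, and Protocol 9.2.1 requires a detailed narrative for investigator-flagged events. Case-level presentation suits sparse events. Adjudication is blinded and conservative, so a later count would not bias it.

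Much of this stands and limits the point. A reader might infer that the trial has no by-arm information at all on corticosteroid harm; the planned tables show otherwise. A reader might also infer that first place in Protocol 5.3 makes this the leading safety endpoint, or that the research hypothesis calls for a between-arm test of corticosteroid harm. List order is not rank, and Protocol 3.3.2 asks only that a favourable safety profile be maintained. Nor can one infer that Listing 7-6 will lack treatment group: the SAP gives no shell for it, and Protocol 11.3.6.1 opens by saying that maintenance-phase events are presented by arm.

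What does not stand is that the existing tables replace the missing one. They do not carry the panel's decision, and assembling a count by hand is not a pre-specified analysis. Sparse events argue for keeping the listing; they do not argue against a count with its denominator.

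**Conclusion.** The concern holds as a reporting gap. The adjudicated set has a dedicated blinded panel and a place among the safety assessments, yet the plan specifies no number of subjects, percentage or exposure-adjusted rate for it by arm. It should be closed, but it affects no efficacy conclusion and no error rate, and the underlying events are reported.

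Its size can only be illustrated. With about 272 per arm, zero events would bound the risk at about 1.1% (one-sided 95%). That figure assumes equal arms, a safety set equal to those randomised, and complete follow-up. Allowing for the protocol's drop-out assumption gives about 1.3 per 100 patient-years. Neither figure predicts what the trial will observe.

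A reader might go further and say that exposure and rescue use do differ between arms. The documents support only that withdrawals might differ, which is reason enough to report a rate beside the percentage.

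**What to change.** In SAP 5.5.3.1, keep Listing 7-6 and add:

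- One table of adjudicated events by randomised arm for the randomised phase, following Shell 63: subjects n (%), events, and rate per 100 patient-years. The shell's footnote names the maintenance phase and would need to name the randomised phase.
- One table by remission or relapse period for the maintenance phase, following Shell 64.
- A column for exact 95% confidence intervals in both. Those shells have none, so this is a small addition to the template.
- Adjudicated events with onset in the open-label phase shown separately. The panel reviews events from the first dose of product, and open-label events do not belong to a randomised arm.

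Protocol 12.1 already defines the event set and the rule for disagreement, so no new data are needed. The cost is one or two extra tables, with wide intervals if events are few. Intervals are not planned for any other adverse event category, so the text should say that they describe precision and do not reinstate the between-arm tests that SAP 5.5.3 dropped.

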11.3.6.2 Rebound

Rebound will be defined as (i) an m-PASI ≥ 12 AND an increase in m-PASI of $\geq 125\%$ of the baseline value, or (ii) new pustular, erythrodermic or more inflammatory psoriasis either a) within 2 months after discontinuation of once-daily treatment in the initial open-label phase, b) within 2 months after discontinuation of once-daily relapse treatment, or c) within 2 months after end of maintenance treatment (up to Visit FU3)

Number of rebounds within two months after entering the maintenance phase will be summarised by treatment group in a table.

Number of rebounds occurring after the first two months of maintenance treatment (i.e. including the follow-up period) will be summarised by treatment group in another table.

Subjects with m-PASI $\geq 125\%$ of baseline (Visit1) score and cases of rebound will be listed.

11.3.6.3 Local safety and tolerability

The local safety and tolerability signs perilesional erythema, perilesional oedema, perilesional dryness, and perilesional erosion, as well as the symptom 'application site burning or pain'

will be summarised over time both for the open-label treatment phase, and for the maintenance phase by treatment group.

11.3.6.4 ACTH-Challenge test

For the group of subjects undergoing the ACTH-challenge test, the number of subjects with serum cortisol concentration values ≤ 18 mcg/dl 30 minutes after the ACTH-challenge test will be summarised over time by treatment group.

11.3.6.5 Vital Signs and Physical Findings

The change in vital signs (blood pressure, heart rate, body temperature) from baseline to end of treatment phase will be summarised.

The change in vital signs (blood pressure, heart rate, body temperature) from randomisation to end of trial will be summarised.

11.3.6.6 Clinical Laboratory Evaluation

The change in each of the laboratory parameters from baseline to end of open-label treatment phase will be summarised as mean, SD, median, minimum and maximum values.

The change in each of the laboratory parameters from randomisation to end of trial will be summarised as mean, SD, median, minimum and maximum values for each treatment group.

Laboratory parameters will be classified as ‘low’, ‘normal’ or ‘high’, depending on whether the value is below, within or above the reference range, respectively.

A shift table will be produced showing the categories at baseline against those at end of treatment period.

A shift table will be produced showing the categories at randomisation against those at end of trial.

To identify subjects with clinically important laboratory changes in albumin-corrected serum calcium levels, LEO has defined threshold levels for concern for a clinically significant change based on the CTCAE v4.0 for grading of specific clinical laboratory results. These LEO-defined threshold levels correspond to a grade of at least ‘moderate’ (i.e. at least 2 on a 5-point scale) according to the CTCAE v4.0. The low threshold level for the albumin-corrected serum calcium is ‘ <2.0 mmol/l’ and the high threshold level is ‘ >2.9 mmol/l’.

Additional shift tables as described above will be produced for clinically significant values of albumin corrected serum calcium as defined by LEO, i.e., <2.0 mmol/l (low threshold) or >2.9 mmol/l (high threshold), i.e. the shift tables will be for subjects with at least one clinically significant value of albumin corrected serum calcium. .

Subjects with laboratory parameters outside the reference range will be listed.

11.3.7 Interim Analysis

No formal interim analyses are planned. However, analysis of the data from the open-label treatment phase might be performed prior to finalising the trial. This will have no impact on the continued conduct of the study nor the interpretation of the results as the open-label treatment phase is not blinded.

11.3.8 General Principles

All significance tests will be two-sided using the 5% significance level. All confidence intervals will be presented with 95% degree of confidence.

An observed cases approach will be used for tabulations of data by visit (i.e. involving only those subjects who attended each specific visit).

Categorical data will be summarised using the number and percentage of subjects in each category and treatment group. Continuous data will be summarised using the mean, median, standard deviation (SD), minimum and maximum values.

All the analyses specified in the protocol will be reviewed in relation to the blinded data actually obtained and the statistical analysis plan update will be finalised before breaking the randomisation code.

The randomisation is stratified by treatment group, trial site, HPA axis testing and disease severity at baseline as factors. Usually, the statistical analysis of efficacy parameters takes all the stratification factors into account. However, the HPA axis test is a safety parameter, which is only determined at a small subset of sites and subjects. Hence stratification by HPA axis test is not applicable for all sites. Also, it is expected that two subjects per site will be randomised. This means that a statistical model having HPA axis testing as a factor may not converge, depending on whether subjects participating in the HPA axis test drop out. Furthermore, the inclusion criteria for participating in the HPA axis test are “Moderate” or “Severe” in the baseline PGA assessment and a baseline BSA between 10 and 30%. Including the stratification factor HPA axis testing would therefore introduce a confounding with the

stratification according to baseline PGA as well as sites. Therefore the stratification according to HPA axis testing is not included in the statistical analyses.

Any changes from the statistical analysis planned in this clinical trial protocol will be described and justified in a protocol amendment/the statistical analysis plan update and/or in the clinical trial report dependent on the type of deviation.

